This is a phase II proof of concept (POC), multi-center, prospective, randomized, placebo-controlled, Sequential Parallel Comparison Design (SPCD) study, in which a total of 60 subjects with schizophrenia will be randomized studywide.

The study will be conducted in two phases. The study treatment will be administered in a double-blind fashion for all subjects throughout both phases of the study. A total of 60 subjects with schizophrenia will be randomized in a 1:1:1 ratio to one of three treatment sequences: drug-drug, placebo-drug, or placebo-placebo. Subjects will be randomized directly following confirmation of eligibility (at completion of Visit 2). Subjects randomized to the drug-drug sequence (n=20) will receive i.v. sodium nitroprusside (0.5 µg/kg/min for 4 hours) at Day 0 and Day 14. Subjects randomized to the placebo-drug sequence (n=20) will receive i.v. placebo at Day 0 and i.v. sodium nitroprusside (0.5 µg/kg/min for 4 hours) at Day 14. Subjects randomized to the placebo-placebo sequence (n=20) will receive i.v. placebo at Day 0 and again at Day 14. The double-blind treatment will be divided into two phases: Phase 1 from Day 0 to Day 14, and Phase 2 from Day 14 through Day 28.

At the end of Phase 1 the randomized subjects will be assessed and categorized into responders and non-responders, based on 20% or more reduction in their PANSS total score between Visit 4 (Baseline, Day 0) and Visit 7(Day 14). The data from the subjects deemed placebo non-responders in Phase 1 who go on to either stay on placebo or to receive treatment with sodium nitroprusside will be pooled with the data from Phase 1 from all subjects, according to SPCD.

Figure 1 –

Nitroprusside SPCD Study Design

Efficacy analysis is based on results of the 10 groups in green boxes

[figure not shown]
[figure not shown]

Figure 2 – Study Schemata

Study Visit Overview

Screening

- Visit 1 (Screening Visit, Day -28 to -14): Consists of signing a HIPAA compliant informed consent form and study qualification based on evaluation of inclusion/exclusion criteria. Medical records will be requested from the participant's primary care physician for confirmation of relevant eligibility criteria.
- Visit 2 (Remote Independent Interview, Day -13 to -3): Consists of independent assessment to confirm the diagnosis and the appropriateness of the subject for the study. Eligibility will also be assessed at this visit by conducting a PANSS,

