historical treatments across mood and psychotic disorders. It allows extraction of other historical measures for antidepressants: ATRQ (Fava and Davidson, 1996; Fava, 2003); for lithium: the Alda Scale (Grof JCP 2002): The questionnaire captures treatment duration, response, and reason for discontinuation. In the present study, FAST is a means of recording number and type of prior antipsychotic trials, to define treatment resistance for purposes of stratification.

SAFER Rater Assessment

In order to confirm diagnosis and to ensure patients are appropriate for the study, remote diagnostic assessments (SCID-I/P Psychosis module), and disease severity assessments (PANSS, MGH FAST, and CGI-S) will be performed remotely by an independent MGH CTNI rater. The subject will be provide contact information and a SAFER interview will be scheduled within 27 days of Visit 1 (screening). Sites will be notified of the results within 24 hours of the interview.

Efficacy Measures

The Positive and Negative Syndrome Scale (PANSS) (Kay, 1987) will be used to measure symptom severity in this trial. PANSS is a 30-item questionnaire used to evaluate schizophrenia symptoms, based on the clinical interview as well as reports of family members or primary care hospital workers. PANSS consists of Positive scale (7 items), Negative scale (7 items), and General Psychopathological scale (16 items) sections. Each item (symptom) will be scored on a 7-point scale with higher scores representing increasing levels of psychopathology: 1) Absent, 2) Minimal, 3) Mild, 4) Moderate, 5) Moderate severe, 6) Severe, and 7) Extreme.

Each of the 30 items is accompanied by a specific definition as well as detailed anchoring criteria for all seven rating points. Ratings will be performed by the Investigator or qualified sub-Investigator. The highest applicable rating point is always assigned, even if the subject meets criteria for lower points as well. In judging the level of severity, the rater must utilize a holistic perspective in deciding which anchoring point best characterizes the subject's functioning and rate accordingly, whether or not all elements of the description are observed. The determined results must be documented on the source documents and in the CRF.

For the purpose of this study, the total PANSS score along with sub-scores for Positive scale, Negative scale, General Psychopathology scale, and Composite scale will be derived as follows:

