Given that subjects with renal disease, cardiac disease, hypotension or medications that destabilize blood pressure will be excluded from the study, and that the infusion rate of SNP for subjects randomized to active drug in this study will be low (0.5 $\mu\text{g}/\text{kg}/\text{min}$), the risk of excessive hypotension and cyanide toxicity is low.

Sodium nitroprusside does have some potential for drug-drug interactions. The hypotensive effect of sodium nitroprusside is augmented by that of most other hypotensive drugs, including ganglionic blocking agents, negative inotropic agents, and inhaled anesthetics. Subjects taking any of these drugs will be excluded from the study. Patients will also be advised not to take these medications during the course of the study.

Infusion Monitoring and Discharge Procedures

The study treatment will be infused with a volumetric infusion pump and the blood pressure of a subject will be continuously monitored by a cardiologist, anesthesiologist, or medically qualified designate as per institutional guidelines. A study physician will be available for consultation on any participant safety issues that arise during the infusion. Each participant will be allowed to rest in a semi-recumbent position. Each subject will receive an intravenous line. The study treatment will be infused with a volumetric infusion pump and the blood pressure of a subject will be continuously monitored by a cardiologist, anesthesiologist, or medically qualified designate as per institutional guidelines. To maintain the double blind, each subject will receive an infusion for 4 hours. Nitroprusside or placebo will be administered at the dose specified in the randomization scheme. Subjects will have one-to-one nursing care during the infusion of the study treatment.

The assigned nurse or medically qualified designate will perform the following monitoring procedures, as developed by the consulting cardiologist:

- Pre-Infusion: 12-Lead ECG (Time -1 to Time 0, baseline)
- During Infusion:
 - 12-Lead ECG @ 30 min
- Post-Infusion:
 - 12-Lead ECG @ 60 min post-infusion
- Vital Signs: BP, HR and O2 sat (same arm, non-IV arm)
Pre-Infusion (baseline)
During Infusion:
 - Q5 min Xs 30 minutes then Q10 min Xs 3.5 Hrs (210 min)
- Post-Infusion:
 - Q5 min Xs 30 minutes then Q10 min Xs 1.5 Hrs (90 min)

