Subjects will receive either sodium nitroprusside diluted with 5% dextrose and infused at a rate 0.5 µg/kg/min for 4 hours, or a placebo solution of 5% dextrose infused over 4 hours. The study treatment will not be exposed to light prior to and during the infusion as exposure of SNP to light has the potential to form cyanide ions. Subjects will be recumbent and blood pressure, heart rate, blood oxygen saturation, and ECG will be continuously monitored during infusion of the study treatment.

Study Product Supplies and Administration

The Institutional Pharmacy will issue either undiluted sodium nitroprusside in sterile 5% dextrose or sterile 5% dextrose only. For subjects randomized to sodium nitroprusside, an unblinded pharmacist will dilute the SNP with 5% dextrose to achieve a concentration allowing infusion of 0.5 µg/kg/min over the course of 4 hours.

Packaging and Labeling

Sodium nitroprusside or placebo will be prepared within 12 hours from the scheduled delivery time and once prepared in solution will be protected from UV light by covering the iv bag with an aluminum foil bag. The intravenous drip chamber will also be covered for blinding purposes but the tubing does not need to be covered.

A study label that includes the subject ID and randomization ID will be pasted to the foil bag so that it is clearly visible. The dextrose solution will also be covered with an identical foil bag and study label so that medical personal administering the i.v. will be blinded to the study treatment.

Dose Modification during Treatment

As previously stated, the subject's blood pressure will be monitored continuously during the study treatment. If the subject's systolic blood pressure falls below 90 mm Hg the

infusion rate will be reduced by 50% and a drop below 80 mm Hg will terminate the infusion. Nitroprusside has a circulating half-life of 2 minutes and blood pressure is usually restored within 1-5 minutes of stopping the infusion. Trendelenburg position and IV fluids will be used if subjects experience symptomatic hypotension. The medical monitor will receive all safety data within 24 hours after each infusion and will inform the PI who will inform the IRB of any safety concerns.

Possible Drug Interactions

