Treatment (infusion) discontinuation will be determined by the criteria outlined in the Infusion Monitoring and Discharge Procedures section of this Protocol. A study physician will be available for consultation on any participant safety issues that arise during the infusion.

A patient who decides to discontinue participation in the study will always be asked about the reason(s) and the presence of any AEs. If possible, they will be seen and assessed by an investigator. AEs will be followed up until resolution.

Procedures for Discontinuation from Study:

If a patient discontinues from the study before randomization, then no further follow-up will be expected. However, if the patient discontinues after randomization, but before receiving any study treatment, the patient will be asked to return for a final study visit, during which the procedures outlined in the Visit 9 Final Visit/Early Termination Visit procedures will be completed, including AEs and concomitant medication assessments.

If a patient discontinues from the study before completion and has received the dose of study drug, the patient will be asked to return for a final study visit, at which the procedures outlined in the Early Termination Visit will be completed. Every effort should be made to follow up with patients who discontinue from the study prior to Visit 9 (Day 28). If patients refuse to return to the clinic for the study-related assessments, a modified follow-up through, for example, regular telephone contact or a contact at study closure should be arranged, if agreed to by the patient and in compliance with local data privacy laws/practices. If the patient refuses follow-up, the reason for the refusal and last contact date should be documented in the eCRF and source documents.

Patients who discontinue from the study will not be replaced.

If an Early Termination Visit is warranted, the following procedures will be performed:

- Concomitant medications
- Vital Signs
- 12-lead ECG
- Anthropometrics (weight, height, waist circumference, BMI)
- CBC with differential and Comprehensive Metabolic Panel (CMP)
- Urinalysis
- Serum Pregnancy test
- PANSS
- CGI-S

- CGI-I
- AE/SAE assessment
- AIMS
- SAFTEE
- C-SSRS
- MATRICS
- UPSA-B

Unblinding Procedure

Methods for Ensuring Blinding

The investigator, subject, and study staff will be blinded. The preparation and labeling of the study drugs will be performed by the site pharmacy in a way to ensure blinding throughout the study.

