No members of the study team at study sites, will have access to the randomization scheme during the conduct of the study, with the exception of the Site's unblinded pharmacist or nurse as designated by the PI.

The randomization schedule for blinding of randomized treatment will be maintained by MGH CTNI or representative and will not be disclosed until after database lock.

During the infusion visits, the study staff conducting the clinical efficacy assessments must not be able to view the bag containing the infusion solution to ensure that they remain blinded. The bag must be protected from view with an opaque covering.

Methods for Unblinding the Study

Individual treatment codes, indicating the treatment randomization for each randomized patient, will be available to the investigator(s) or pharmacists from MGH CTNI or its designee.

The treatment code must not be broken except in medical emergencies when the appropriate management of the patient necessitates knowledge of the treatment randomization. The investigator documents and reports the action to MGH CTNI or representative, without revealing the treatment given to the patient to MGH CTNI or representative's staff.

MGH CTNI retains the right to break the code for serious adverse events (SAEs) that are unexpected and are suspected to be causally related to a study drug and that potentially require expedited reporting to regulatory authorities. Treatment codes will not be broken

for the planned analyses of data until all decisions on the evaluability of the data from each individual patient have been made and documented.

J. ETHICAL CONSIDERATIONS

Risk/Benefit Assessment

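### The infusion bag and drip chamber are covered but the tubing is exempted; the same opaque cover on the whole line in both arms would be a cheap precaution for the blind

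*Protocol*

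**What the plan says.** Protocol section I, Packaging and Labeling, puts the prepared bag in aluminum foil to keep out UV light. The dextrose gets a matching foil bag and label, "so that medical personal administering the i.v. will be blinded to the study treatment". On the rest of the line it says: "The intravenous drip chamber will also be covered for blinding purposes but the tubing does not need to be covered".

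Under Dosing, the same section says: "The study treatment will not be exposed to light prior to and during the infusion". The reason given is that light can cause the drug to form cyanide ions.

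Under Methods for Ensuring Blinding, the protocol states that investigator, subject and staff are blinded, and adds: "The preparation and labeling of the study drugs will be performed by the site pharmacy in a way to ensure blinding throughout the study". For infusion visits it says that "the study staff conducting the clinical efficacy assessments must not be able to view the bag containing the infusion solution", and it requires an opaque covering for the bag. That rule mentions neither the drip chamber nor the tubing.

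Section H, Infusion Monitoring and Discharge Procedures, describes who is at the bedside: "Subjects will have one-to-one nursing care during the infusion of the study treatment". A research assistant and a research nurse are also present throughout.

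**The concern.** The sponsor gives blinding as its reason for covering the drip chamber. The tubing holds the same liquid, runs to the subject's arm and stays in view for 4 hours. If the look of the solution is reason enough to hide the chamber, the same reason applies to the tubing. The protocol does not explain why the two are treated differently.

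The primary endpoint is the PANSS total score. Section H, Efficacy Measures, says "PANSS is a 30-item questionnaire used to evaluate schizophrenia symptoms, based on the clinical interview", so a subject who has guessed the treatment could influence the score even if the rater has seen nothing.

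The sequential design adds a second exposure. Section F says: "Subjects randomized to the placebo-drug sequence (n=20) will receive i.v. placebo at Day 0 and i.v. sodium nitroprusside" at Day 14. In the Stage 2 comparison the other group receives placebo twice. If the solutions differ visibly, only the placebo-drug subjects would see the line change between infusions.

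**Working it through.** **1. Which part of the line is protected, and from whom**

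| Part | Covered? | Named in the rater rule? |
|---|---|---|
| Bag | Yes, foil in both arms | Yes |
| Drip chamber | Yes, for blinding | No |
| Tubing | Expressly exempted | No |

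No other section of the protocol or SAP screens the tubing from the subject, the nurse or the research assistant. The general statement about pharmacy preparation and labeling does not deal with what can be seen at the bedside. Staff are near the line often: section H schedules vital signs every 5 minutes for 30 minutes and then every 10 minutes for 210 minutes, which is 30/5 + 210/10 = 6 + 21 = 27 checks per infusion.

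**2. The plan's own power figure**

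Inputs from section M, Sample Size Determination and Rationale: SD 14; differences of 9 (Stage 1) and 11 (Stage 2); weight 0.5; 20% attrition; 30% placebo response; two-sided 0.05. Stage 1 compares 20 with 40.

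- Stage 1 SE = 14 × √(1/20 + 1/40) = 3.834
- Stage 2 n per arm = 20 × 0.8 × 0.7 = 11.2; SE = 14 × √(2/11.2) = 5.916
- Weighted SE = 0.5 × √(3.834² + 5.916²) = 3.525
- Weighted difference = 0.5 × 9 + 0.5 × 11 = 10
- Power = P(Z > 1.96 − 10/3.525) = 81.0%, against the stated 81%

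**3. What a bias would do (illustration)**

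The documents give no size for such a bias, so b = 1, 2 and 3 points toward the drug are assumptions. With no true effect, the two-sided rejection rate is P(Z > 1.96 − d/3.525) + P(Z < −1.96 − d/3.525). Here d = 0.5b if the bias is in Stage 2 only, and d = b if it is in both stages.

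| b (points) | Stage 2 only | Both stages (worst case) |
|---|---|---|
| 0 | 5.0% | 5.0% |
| 1 | 5.2% | 5.9% |
| 2 | 5.9% | 8.8% |
| 3 | 7.1% | 13.6% |

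With 16 v 32 in Stage 1 and 11 v 11 in Stage 2, the SE is 3.675. The rates for b = 1, 2 and 3 are then 5.2%, 5.9% and 6.9% (Stage 2 only) or 5.9%, 8.5% and 12.9% (both).

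An error of 10% needs d = 2.30. That is b = 4.6 in Stage 2 alone (4.6/11 = 42% of the assumed Stage 2 effect) or 2.3 in both stages.

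**4. Could the rater see the line?**

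The synopsis puts the infusion-visit PANSS at Hour 3 to 4, while the infusion is running. The Visit 4 and Visit 7 procedures in section H put it between hours 4 and 7, after the infusion. Raters would be exposed only on the synopsis timing. The subject and bedside staff are exposed either way.

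**The case against.** The strongest objection is that the key premise is missing. Neither document says that the diluted drug looks different from 5% dextrose. The only internal hint is the covered drip chamber, and the sentence that covers it also exempts the tubing. That reads as a deliberate choice, and the documents do not show it to be wrong. This stands, and it limits the point to a precaution.

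Exposure is also limited. Section H assigns PANSS ratings to the investigator or a qualified sub-investigator and has psychiatry research staff administer the scales. What the nurse sees reaches the endpoint only if it is passed on. At Day 0 a subject has no earlier infusion for comparison, so bias in Stage 1 needs the further assumption that the subject knows what the drug should look like. That is why the both-stage figures are a worst case.

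The error table would be the same for a bias from any cause, so it is not evidence about tubing. Other cues also remain after the fix: blood pressure, heart rate, headache and dose reductions. These objections are fair. They bear on how much the fix would gain. They are not a reason to leave an avoidable visual cue in place, and they do not resolve the tension with the light rule.

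**Conclusion.** The gap in the text is real. The tubing is exempted without a stated reason, the rater rule stops at the bag, and nothing else screens the line. The exemption also fits poorly with the rule on light during infusion, whatever the solutions look like.

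The size of the risk is unknown. For a bias to arise, a difference would have to be visible, noticed, read correctly and remembered until the two-week rating, which for Stage 2 is the Day 28 outpatient visit. If the solutions cannot be told apart, the bias is zero. The figures above are illustrative and rest on assumed biases.

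A reader might infer three stronger claims that the documents do not support:

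- **That the blind is broken.** Nothing in the documents says that the solutions can be distinguished.
- **That any unblinding would go unreported.** Section H collects arm guesses from subjects and clinicians at the end of the study. General Statistical Considerations and Statistical Methods, in both documents, plan frequencies and percentages for categorical data, by treatment group. A summary of the guesses is therefore covered in general terms, although none is named.
- **That the Schedule of Events settles the Visit 7 PANSS timing.** Its columns cannot be aligned reliably in the available text. The Visit 4 and Visit 7 procedures are the firmer source.

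The change is worth making because it costs little and protects an interview-based primary endpoint.

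**What to change.** 1. In section I, Packaging and Labeling, replace the exemption with: *The bag, drip chamber and full length of tubing will be covered with the same opaque covering in both arms.* This also brings the section into line with its rule on light.
2. In section I, Methods for Ensuring Blinding, extend the rater rule from the bag to the bag, drip chamber and tubing.
3. As a side correction, change the synopsis timing of the PANSS at Visits 4 and 7 from Hour 3 to 4 to hours 4 to 7, as in the section H visit procedures.

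Cost: three wording changes and at most 60 × 2 = 120 sleeves. Of these, 20 × 2 + 20 = 60 are for drug infusions and 60 for placebo. The downside is that visual inspection of the line becomes slightly harder. No visits, subjects or assessments are added, and sample size and power do not change.

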A 10-minute run-in period ("Phase I") has been added to ensure that the patient tolerates the drug. As determined by consulting cardiologist, this will include the administration of the drug at half of the rate (0.25 mcg/kg/min). The following Safety parameters will be followed for Phase I:

Safety Parameters

Safety Parameters Phase I dose:

- If SBP \leq 89 STOP infusion. Lie flat, feet up, call N.P. & P.I.
- If HR $>$ 120 bpm or $>$ 20 bpm over baseline HR, abort study
- If SpO2 $<$ 92%, stop infusion
- If patient reports headache, ask: "do you feel this headache is tolerable?"
 - If patient says "yes," continue dose
 - If patient says "no," STOP dose

-If patient experiences symptomatic hypotension (nausea, dizziness) STOP infusion.

If Phase I is tolerated per the above guidelines after the 10 minute run-in period, the drug will be administered at the rate of 0.5 mcg/kg/min ("Phase II") with the following parameters:

Safety Parameters for Phase II dose:

- If SBP between 81 and 89, lower dose to Phase I dose for 15 min. Monitor with CRC NP.
- If SBP rises to > 89mm Hg continue Phase I dose
- If SBP remains between 81 and 89mm Hg abort and call P.I.
- If SBP < 80, STOP infusion, lie flat, feet up & call P.I.
- If HR > 120 bpm or > 20 bpm over baseline HR, lower dose to Phase I dose for 15 min
- If SpO2 < 92% Stop infusion
- If patient reports headache, ask, "Do you feel this headache is tolerable?"
 - If patient says "yes", continue dose
 - If patient says "no", *lower dose to Phase I dose for 15 min*
- If better, continue Phase I dose
- If still intolerable, STOP dose
- If patient experiences symptomatic hypotension (nausea, dizziness) *lower dose to Phase I dose for 15 min*
- If better, continue Phase I dose
- *If not, Stop infusion, call P.I.*

Should the patient require PRN rescue medications, the following procedures will take place:

PRN Rescue medications:

In consultation with CRC N.P.

For SBP < 80 mmHg, may give 250 ml 0.9% NS

IV bolus via Sigma pump @999 ml/hr over 15 min X 2

For rash may give

Diphenhydramine 25 mg by mouth X 1

The IV line will be left in place for at least 1 hour following the infusion to allow for additional medications to control emergent side effects. If additional IV medication is necessary, an anesthesiologist, cardiologist, or medically qualified designate will start the infusion and a medical team will be present during the entire infusion period.

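### Two protocol sections give different rescue instructions for hypotension during the infusion, and no rule reconciles them

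*Protocol*

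**What the plan says.** Two places in the Protocol tell staff what to do about hypotension during the infusion.

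**Section I, Dose Modification during Treatment.** If SBP falls below 90 mmHg, the "infusion rate will be reduced by 50% and a drop below 80 mm Hg will terminate the infusion". It then adds: "Trendelenburg position and IV fluids will be used if subjects experience symptomatic hypotension". The rescue trigger is symptoms, the wording is mandatory, and no pressure is attached.

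**Section H, Infusion Monitoring and Discharge Procedures.**
- PRN rescue list: "For SBP < 80 mmHg, may give 250 ml 0.9% NS", introduced by "In consultation with CRC N.P". The trigger is pressure, the wording is permissive, and symptoms are not mentioned.
- Symptoms during the half-rate run-in: "If patient experiences symptomatic hypotension (nausea, dizziness) STOP infusion".
- Symptoms at full rate: "If patient experiences symptomatic hypotension (nausea, dizziness) *lower dose to Phase I dose for 15 min". If the subject improves, the lower rate continues; if not, the infusion stops and the investigator is called.
- Pressure at full rate: "If SBP < 80, STOP infusion, lie flat, feet up & call P.I". The run-in has a similar step at SBP of 89 or less.

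**Precedence.** Section I, Medical Reasons for Discontinuation, says: "Treatment (infusion) discontinuation will be determined by the criteria outlined in the Infusion Monitoring and Discharge Procedures section of this Protocol".

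The SAP repeats the Protocol's data analysis section and says nothing on rescue.

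**The concern.** The Protocol's safety rationale names excessive hypotension as one of the two most important adverse reactions to the drug. About four sites need one instruction for it. As written, the two sections differ both on what triggers fluids and on whether fluids are compulsory.

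Two consequences bear on the data. First, change in blood pressure is a listed safety assessment in the Protocol and the SAP. If fluids depend on which section a site works from, readings after a hypotensive event could vary with site practice. Second, Table 3 of the Protocol gives departure from the safety management plan as an example of a major violation, and the Per Protocol population excludes subjects with major violations. A site that follows one section could be judged to have departed from the other, which could change membership of the supportive analysis population.

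**Working it through.** The plan gives no figure to reproduce, so the check is a comparison of the two texts by case.

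| Case | Section H (Infusion Monitoring) | Section I (Dose Modification) | Comparison on fluids |
|---|---|---|---|
| Symptoms, SBP 80 or above, run-in | Stop. The symptom step lists no fluids or positioning; the pressure step adds lying flat with feet up if SBP is 89 or less | Fluids and Trendelenburg required | Not listed v required |
| Symptoms, SBP 80 or above, full rate | Lower the rate for 15 min, then continue at that rate or stop and call the investigator. No fluids or positioning listed | Fluids and Trendelenburg required | Not listed v required |
| Symptoms, SBP below 80 | Stop, flat with feet up; saline optional | Infusion terminated; fluids and Trendelenburg required | Optional v required |
| No symptoms, SBP below 80 | Stop, flat with feet up; saline optional | Infusion terminated; silent on fluids | Optional v silent: different triggers, no contradiction |

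**Does any passage reconcile them?** The precedence sentence gives section H authority over stopping the infusion. It does not mention fluids or positioning. Section I refers back to earlier text only for the continuous monitoring of blood pressure. Neither rescue instruction refers to the other.

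**Exposure.** From the 1:1:1 allocation in Study Design (20 subjects per sequence, two infusions each):
- all infusions: 60 × 2 = 120;
- active infusions: 20 × 2 (drug-drug) + 20 × 1 (placebo-drug) = 60.

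These are maxima before attrition. The only event figure in the Protocol at this dose is no hypotension in 10 treated subjects in the cited pilot trial. With 0 of 10, the exact one-sided 95% upper limit is 1 − 0.05^(1/10) = 1 − 0.741 = 0.259, about 26%. That limit is for hypotension of any kind, so the pilot neither rules the disputed event out nor estimates its frequency.

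**Recording.** Concomitant Therapy already requires every medication and therapy to be recorded with dose, route, indication and start and stop dates. Clock time is not listed. Scheduled blood pressure readings in section H are 30/5 + 210/10 = 6 + 21 = 27 during the infusion and 30/5 + 90/10 = 6 + 9 = 15 afterwards, so 27 + 15 = 42 (plus the pre-infusion reading) on a single date. A date alone cannot show which of them came after a fluid bolus.

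**The case against.** The best defence is that silence is not prohibition. Section H does not bar fluids at 80 or above, and section I does not bar them in a symptom-free subject below 80. Section H also keeps the line in place for at least an hour after the infusion in case further medication is needed. A site that reads both sections can satisfy both by giving fluids for symptoms and treating them as optional below 80 otherwise. This stands, and it rules out two stronger readings that a reader might infer: that section I withholds fluids from a symptom-free subject at, say, 78 mmHg, and that subjects with the same event will in fact receive different rescue. The text supports only that they could.

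It does not remove the inconsistency. A site that uses section H's option not to give saline to a symptomatic subject below 80 complies with section H and breaches section I. A site that completes section H's steps for a dizzy subject at 85 mmHg has omitted something section I requires.

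Three further points stand in part. Section H's response to symptoms is more than a rate cut: it goes on to stop the infusion and call the investigator if the subject does not improve, and in the run-in it stops at once. Any fluid given would affect later readings under any rule, including a reconciled one; what the discrepancy adds is variation by site. And most of the recording needed already exists.

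**Conclusion.** The point holds as an internal inconsistency. For symptomatic hypotension, sections H and I disagree at every pressure: fluids are required against not listed at SBP of 80 or above, and required against optional below 80. Nothing in either document settles which applies.

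Its size is modest. The instructions cover up to 120 infusions, but the number of events in dispute cannot be estimated from the documents. Sample size, power, Type I error and the PANSS endpoints are unaffected.

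A reader might also infer a threat to blinding, because a fluid bolus is visible to staff. The documents do not support that as a separate harm: both sections already include rate cuts or stops for low pressure, and no added effect of fluids is shown.

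The verdict rests on two readings: that section I's silence on pressure means no threshold was intended, and that some sites may work mainly from one section. It is worth correcting because hypotension is a key named risk and the correction is cheap. Nothing here says which instruction is clinically right.

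**What to change.** Reconcile the rescue text in Infusion Monitoring and Discharge Procedures with that in Dose Modification during Treatment. Keep one rescue rule, in one section, with the other referring to it. The rule should state the trigger (pressure, symptoms or both), whether fluids are optional or required, and where positioning applies. The clinical team must decide the content. Either extend the precedence sentence under Medical Reasons for Discontinuation to rescue measures, or make it unnecessary by the cross-reference. Any alignment of the infusion-rate thresholds in the same two sections can be made in the same edit, but would not by itself settle the fluid rule.

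For the data, add the clock time of any fluid given to the existing therapy record, and flag later blood pressure readings from that visit in the safety tables.

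The cost is a short protocol wording change, one added CRF field and one footnote or flag in the safety tables. The design, sample size and efficacy analysis do not change.
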